Primary Objectives	
(1) To determine the preferred recruitment venue and testing modality that targets and finds the highest number of HIV infected and at risk female youth aged 15-24 years in Homa Bay County, Nyanza region, western Kenya (Aim 1).
 
 • This will be determined by examining the uptake and yield of previously undiagnosed HIV infection of the two (2) 'seek' strategies (community or home-based) and the three (3) 'test' strategies (self-testing, HTS in a home/mobile setting, or facility-based HTS) among female youth; 
(2) To conduct an economic evaluation, using cost effectiveness analyses to determine the relative utility of each seek, test, link, and prevention intervention (Aim 3).

Secondary Objective	
(1) To pilot and evaluate an adaptive intervention to link newly diagnosed HIV-positive female youth to treatment and care services (Aim 2a);
 
(2) To identify barriers and facilitators to seeking HIV care services after receiving a positive diagnosis (Aim 2b);
 
(3) To identify barriers and facilitators to seeking HIV prevention services for high risk female youth after receiving a negative HIV test result (Aim 2c);

	(4) To provide an HIV prevention intervention to a randomly selected subset of high risk negatives (N≈185) (motivational text message, with referral for combination prevention interventions), and to re-test them at 12 months (Aim 2d).

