8. STUDY OBJECTIVES

Primary Objectives

- (1) To determine the preferred recruitment venue and testing modality that targets and finds the highest number of HIV infected and at risk female youth aged 15-24 years in Homa Bay County, Nyanza region, western Kenya. This will be determined by examining uptake and yield of previously undiagnosed HIV infection of the two 'seek' strategies (community or home-based) and the three 'test' strategies (self-testing, HTS in a mobile/home setting, or facility-based HTS) among female youth;
- (2) To conduct an economic evaluation, using cost effectiveness analyses to determine the relative utility of each seek, test, link, and prevention intervention.

Secondary Objectives

- (1) To pilot and evaluate an adaptive intervention to link newly diagnosed HIV-positive female youth to treatment and care services;
- (2) To identify barriers and facilitators to seeking HIV care services after receiving a positive diagnosis;
- (3) To identify barriers and facilitators to seeking HIV prevention services for high risk female youth after receiving a negative HIV test result;
- (4) To provide an HIV prevention intervention to a randomly selected subset of high-risk negatives (motivational text message with referral for combination prevention interventions), and to re-test them at 12 months.

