The sample size for the linkage to care adaptive intervention pilot is an estimate of the number of female youth with previously undiagnosed HIV infection we anticipate reaching. The expected percentage of girls testing positive was based on our MP3 Youth pilot study (data not yet published), and we expect 9% of all tested girls to have HIV infection not previously diagnosed. Thus given a total sample size of 1,200 female youth, we anticipate enrolling about 108 previously undiagnosed HIV positive females in the adaptive intervention pilot to link HIV positive female youth to HIV treatment and care.

Sampling method: We will stratify the sample by conveniently selected sub-counties; Homa Bay municipality, Mbita sub-county and Ndhiwa sub-county. Mapping of catchment areas surrounding health facilities will be used to establish relationships with referral clinics. We select a random starting point that is within walking distance (about 5km) of the catchment area of the health facility. Approximately four hundred (400) participants will be recruited from each stratum and for each stratum it is assumed that 200 participants will be recruited through each recruitment approach. Both recruitment strategies (household and mobile event) will run concurrently until the desired sample size is reached. If needed for sample size attainment, we will expand the sampling area to a 6 - 10 km circumference of the referral clinic.

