13.2 Description of the Analyses

See Table 1: Evaluation Plan for Data Management and Analysis.

Baseline Data

1. Basic demographic information
2. Sexual risk behaviors
3. HIV risk behaviors
4. Attitudes/knowledge about HIV transmission and prevalence
5. Knowledge and acceptability of specific HIV prevention interventions

6. Knowledge and acceptability of family planning methods

The primary endpoint for comparisons of recruitment and testing strategies is newly diagnosed HIV infection. The key outcomes we detail below are broken out by study aims and based on the HIV prevention and treatment continua, which organizes our outcomes of interest by recruitment strategies, testing, linkage, retention and primary prevention.

Primary Endpoints

Primary outcomes of interest for Aim 1 is based on the HIV prevention and treatment continua as outlined below:

- Recruitment/Seek: Ability to identify and recruit female youths that are high risk for HIV infection using two seek strategies (home-based vs. community-based)
 - The proportion of youth in the community who accept study screening (estimated from total youth approached as the denominator);
 - The proportion of youth who accept study enrollment (estimated from youth screened and eligible as the denominator).
- Testing:
 - Testing uptake by different testing modalities;
 - Completion of confirmatory testing;
 - Proportion that are positive;
 - Among those who are positive, completion of baseline collection of CD4 and viral load tests.

Outcomes of interest for the Aim 3 economic evaluation include:

- Compute the cost per HIV-infected female youth identified under each 'seek' strategy (home-based vs. community based);
- Compute the cost per HIV-infected female youth identified under each 'test' strategy (self-testing, staff delivered HTS testing, standard facility-based HTS);
- Calculate the incremental cost-effectiveness ratio of the adaptive linkage to care intervention among HIV positive female youth;
- Compute the cost of the SMS prevention intervention among HIV negative female youth.

Secondary Endpoints

- Linkage to Care:
 - Percent of females who tested positive that attended a first HIV care appointment at an HIV Comprehensive Care Center (CCC)
 - Time to link to care after positive confirmatory test result
- Retention in Care:
 - Completion of viral load testing at 12 months;
 - Reported appointment attendance via SMS and verification by study staff at 3, 6, 9, and 12 months.

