Logistic regression analysis will be used to determine which recruitment and HIV testing approaches yield the highest proportion of newly diagnosed HIV infection. HIV testing result (negative vs. positive) will be regressed on variables indicating recruitment strategy (home vs. community) and type of HIV testing (self, staff-aided, facility-based). With facility-based testing following community-based recruitment as a reference category, we will estimate how home-based recruitment and other testing approaches change the odds of a positive test result. The interaction between recruitment strategy and HIV testing approach will be tested to determine whether the yield of each testing approach is conditional on recruitment strategy. If a significant interaction effect is found, simple main effects of testing approach within each recruitment strategy and simple main effects of recruitment strategy within each testing approach will be estimated. In addition to comparing yield by recruitment strategies and testing approaches, we will consider interaction effects with youth characteristics, such as age, risk behaviors, and HIV testing history, and type of testing. Similar logistic regression analyses will examine differences in the odds of completing all confirmatory testing by recruitment strategy and approach to testing.

Home-based and community-based recruitment strategies will also be compared to determine which strategy is more effective in reaching higher risk female youth. Rates of acceptance of screening among potential participants offered screening and rates of enrollment among eligible participants will be compared by recruitment strategy using logistic regression. Risk will be characterized by number and serostatus of sex partners, concurrency, condom use, and patterns of HIV testing by the participant and any sex partners.

A random selection of N≈185 girls with HIV negative tests will be followed-up. We will assess risk behaviors, condom use, additional HIV testing, linkage to prevention and any new HIV diagnoses over the year since study enrollment. Re-testing, prevention service use, and new HIV will be examined in relation to recruitment strategy, testing approach at enrollment, and participant risk behavior and other characteristics.

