In order to determine costs, we will conduct a micro-costing of the cost per HIV-infected person identified under each ‘seek’ and ‘test’ strategy. This will be followed by an incremental cost-effectiveness analysis of the linkage to care interventions among HIV-infected, and a cost analysis of the SMS intervention among HIV-uninfected, women. These costs will include all costs required to deliver each intervention (home visits, staff time, supplies, and monitoring). Data will primarily utilize a micro-costing methodology that uses project expenditure and management records, employing structured costing spreadsheets that record each resource, category (e.g., personnel, supplies), quantity (e.g., hours), and unit costs. The cost data for the self-test group will include costs of obtaining a confirmatory test for those with positive self-testing results. The cost data will be stratified by HIV testing venue (home based, community based (mobile), or referral facility). With these cost data, we will calculate and compare the cost per HIV-infected person identified in each HTC strategy. We will also evaluate the costs of the linkage interventions per individual successfully linked to care. The results of the economic evaluation will allow us to identify the most efficient, affordable way to seek high risk young women and test them. For the linkage interventions, we will utilize the cost data as well as the effectiveness results to compute the ICER for the novel linkage intervention that is used. The ICER will reveal whether the costs of achieving the incremental gains from additional linkage intervention(s) suggest whether it is cost-effective or not. These results will provide novel data on the cost-effectiveness of linkage to care interventions for high-risk females in sub-Saharan Africa.

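### As coded, the Aim 1 yield model estimates positivity among girls who have a test result; no planned test or interval addresses infections found per enrolled girl

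*Combined protocol and SAP*

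**What the plan says.** - **Objective.** Section 6 seeks the recruitment venue and testing modality that "targets and finds the highest number of HIV infected and at risk female youth". Section 8 adds: "This will be determined by examining uptake and yield of previously undiagnosed HIV infection".
- **Endpoint.** Section 13.2: "The primary endpoint for comparisons of recruitment and testing strategies is newly diagnosed HIV infection". No denominator is given. Table 1 (in Section 15.9) puts N=1200 against the recruitment and testing rows without saying how a girl with no result is scored.
- **Model.** Section 13.2: "HIV testing result (negative vs. positive) will be regressed on variables indicating recruitment strategy (home vs. community) and type of HIV testing", with facility-based testing after community recruitment as the reference category.
- **Separate analyses.** Section 13.2 lists testing uptake by modality as an outcome and includes refusal to test as a category in the preference model. It also says "Similar logistic regression analyses will examine differences in the odds of completing all confirmatory testing by recruitment strategy and approach to testing", and for the economic evaluation "we will calculate and compare the cost per HIV-infected person identified in each HTC strategy".
- **Where tests happen (Section 11.5.1).** Staff-aided testing is done in the home or at the mobile event. Self-testing is done off site within two weeks; non-reporters are phoned and then traced. Facility choosers leave with a referral card naming a contact, and their locator details are collected for follow-up.
- **Sample size.** Section 10.2: "we expect 9% of all tested girls to have HIV infection not previously diagnosed", followed by "Thus given a total sample size of 1,200 female youth, we anticipate enrolling about 108 previously undiagnosed HIV positive females". Section 15.11 bases its detectable odds ratios on all 600 girls recruited per strategy.

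**The concern.** The objective concerns a number of infections found. The outcome in the yield model has two values, negative and positive, and no rule says what happens to an enrolled girl who has neither. As coded she contributes nothing, and the odds ratio describes positivity among completers.

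One option yields its result on the spot and the other two depend on a later step, so completion may well differ between them. If it does, the planned odds ratio can show no difference between options that find different numbers of cases, or can rank them in the opposite order. A reader would have to combine the uptake and positivity results by hand, with no interval for the product. The sample-size statements share the gap: a rate defined per tested girl is applied to every enrolled girl.

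**Working it through.** **1. Reproduce the plan's detectable odds ratios.** Inputs from Section 15.11: 9% base rate, 80% power, 600 per recruitment strategy, equal preference across three options (400 each; 200 each within a strategy). Alpha is not stated; I assume two-sided 5%. Method: two-proportion power with pooled variance, p2 = OR·(p1/(1−p1)) / (1 + OR·p1/(1−p1)).

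For OR 1.67: p2 = 1.67 × (0.09/0.91) / (1 + 1.67 × 0.09/0.91) = 0.1418, and power at 600 per group is 80.0%. OR 1.85 at 400 per group gives 79.8%, and OR 2.32 at 200 gives 80.2%. All three figures reproduce with full group sizes, so they carry no allowance for missing results. Likewise 108 = 0.09 × 1,200.

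**2. Apply a uniform completion rate (assumed).**

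| Completion | Detectable ORs | Expected positives |
|---|---|---|
| 100% | 1.67, 1.85, 2.32 | 108 |
| 90% | 1.71, 1.91, 2.41 | 97 |
| 80% | 1.76, 1.98, 2.53 | 86 |
| 70% | 1.83, 2.06, 2.67 | 76 |

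The linkage pilot's hazard ratio of 2.2 (Section 15.11: 80% re-randomized, 60% linked, 1:1) follows from HR = exp(2 × 2.80/√events). With 108 positives, events = 108 × 0.8 × 0.6 = 51.8 and HR = 2.18. With 86.4 positives, events = 41.5 and HR = 2.39.

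**3. Planned odds ratio against infections found.** Inputs: 400 girls per option (equal preference, Section 15.11); 9% positive among those tested in every option; staff-aided completion 1074/1093 = 98.3% (Section 7.2.1; the earlier pilot, both sexes, staff testing only). Facility completion c is assumed, because the documents give none.

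Staff-aided finds 400 × 0.983 × 0.09 = 35.4. Facility finds 400 × c × 0.09. The per-chooser OR compares the number found out of 400 in each option, with a Wald 95% interval. At c = 40%: (14.4/385.6) / (35.4/364.6) = 0.38.

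| Facility completion (assumed) | Planned OR | Facility finds | Staff-aided finds | Per-chooser OR (95% CI) |
|---|---|---|---|---|
| 40% | 1.00 | 14.4 | 35.4 | 0.38 (0.21 to 0.72) |
| 60% | 1.00 | 21.6 | 35.4 | 0.59 (0.34 to 1.02) |
| 80% | 1.00 | 28.8 | 35.4 | 0.80 (0.48 to 1.34) |

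Only the first interval excludes 1. The gain is an estimate and interval on the relevant quantity, not assured significance.

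**4. Ranking can reverse (illustration).** Suppose self-testing has 12% positivity among 60% completers and staff-aided testing has 9% among all. Among tested girls, OR = (0.12/0.88)/(0.09/0.91) = 1.38, favouring self-testing. Per enrolled chooser, self-testing finds 0.12 × 0.60 = 7.2% against 9.0%, so OR = (0.072/0.928)/(0.09/0.91) = 0.78. With 400 choosers each, that is 28.8 infections against 36.

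**5. Choice share also matters.** In step 3 facility testing finds as many infections as staff-aided testing if 0.983/c times as many girls choose it: 2.5, 1.6 or 1.2 times at 40%, 60% or 80%. Per-chooser yield alone does not identify the option that finds most.

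**The case against.** The strongest reply is that the plan already covers non-completion. The objective names two components, uptake and yield, and both are analysed. Refusal is a category in the preference model, confirmatory completion has its own regression, and cost per infected girl identified does reflect non-completion, since a kit or referral with no result adds cost and no case. Self-testers who do not report are phoned and traced, and facility choosers leave locator details. Much of this stands: a reader might infer that the plan ignores non-completion, and the documents do not support that. What remains is that the preference model concerns the option chosen, the completion regression concerns confirmatory testing, and cost per case mixes completion with cost. None gives an interval for infections found per enrolled girl.

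A reader might also infer that the plan excludes girls without a result. It does not say so. Exclusion follows from the outcome coding, and the endpoint of newly diagnosed infection could be scored yes/no for all 1,200. Section 11.5.1 also gives 1,200 as a testing target, although Section 11.4 stops recruitment at 1,200 enrolled. The supportable statement is that the denominator is unset and the written model conditions on a result.

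Finally, a reader might infer that the study is underpowered. Sections 10.2 and 15.11 present Aim 1 as exploratory, with effects computed from a feasible sample, and the 108 is labelled an estimate. At the earlier pilot's 98.3% the power loss would be under one percentage point. That pilot offered staff testing only, so it does not settle completion for the other options, but the power issue is a small unstated assumption.

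**Conclusion.** The point holds as a mismatch between the written yield model and the objective. The model, as coded, targets positivity among girls with a result; the objective concerns infections found; and no planned analysis supplies a test or interval for the latter. Under the assumed facility completion rates of 40%, 60% and 80%, the planned odds ratio stays at 1.00 while facility testing finds 14, 22 or 29 infections against 35. The real size is unknown: every off-site completion rate here is an assumption, and tracing may keep completion high. The same mechanism could affect the home-versus-community comparison, but these illustrations concern modality only.

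The sample-size part is secondary. The stated odds ratios and the 108 are arithmetically right under full completion; that condition is not stated. The matter is worth settling before results are seen, because the choice of denominator bears on a primary aim.

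**What to change.** In Section 13.2, add a yield model whose outcome is confirmed newly diagnosed HIV (yes/no) among all enrolled girls, by recruitment strategy and by chosen testing option. Count a girl with no completed or confirmed result as not identified. Keep positivity among those tested and test completion by option as reported components. Show the number of infections found and the share of girls choosing each option. Describe modality results as yield by chosen option, not as a causal effect, because girls select their own option.

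In Sections 10.2 and 15.11, add one sentence: the detectable odds ratios (1.67, 1.85, 2.32) and the N of about 108 apply a per-tested 9% to all enrolled girls and so assume that each has a result. Give an example at lower completion (at an assumed 80%: 1.76, 1.98, 2.53 and 86). Section 10.2 prints 2.01 where Section 15.11 has 2.32 for the within-strategy comparison; that separate inconsistency should be reconciled in the same edit.

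The cost is SAP wording, one derived variable and one sentence on sample size, with no new visit or test. It relies on facility results reaching the study, as the planned model already does. The drawback is that the combined outcome mixes completion with positivity, so both components must still be shown.

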7.2 Background

[figure not shown]
HIV in Kenyan Female Youth

In Kenya, HIV prevalence is 5.9% among individuals aged 15-64 (NASCOP, 2014a), and estimated HIV incidence declined by 34% 2001-2011 (UNAIDS, 2012b). HIV prevalence has dropped since 2007 in most regions of Kenya but not in Nyanza region (NASCOP, 2014a), where this study will take place. The prevalence of HIV varies drastically per region in Kenya, with variations between 2.1-15.1% (NASCOP, 2014a). Children and youth aged 0-24 years form 66% of Kenya's population. Surveillance data indicate that most new HIV infections occur among youth ages 15-24, when many are unaware of HIV status, condom and contraceptive use are low, and gender inequalities, concurrent sexual partnerships, and cultural value of childbearing enhance risk (Kenya National Bureau of Statistics (KNBS) and ICF Macro, 2010). The majority of Kenya's population is at high risk for HIV infection and the rest of the population will be affected by reduced productivity, increased medical bills, and strained social support.

Females between ages 20-24 have a risk of HIV infection three times higher than males of the same age (NASCOP, 2014a). The 2010 Kenya Demographic Health Survey (KDHS) showed that prevalence of HIV among females aged 15-19 is 2.7%, and 20-24 is 6.4%, whereas the prevalence of HIV among

males aged 15-19 is 0.7%, and 20-24 is 1.5% (Kenya National Bureau of Statistics (KNBS) and ICF Macro, 2010). Young females have a much higher prevalence of HIV. Figure 1 shows HIV prevalence among women is higher than men from age 17 on and increases linearly with age, but for young men, remains lower and stable until age 24. This pattern underscores the need to focus on preventing HIV among 15-24 year old women. The UN and PEPFAR, among others, have emphasized the need to focus on disproportionately affected populations, such as young females, to have greater impact on HIV control (Birx, 2014a, 2014b). Exploration of sociocultural drivers of the HIV epidemic in Kenya highlights the need for age and gender-specific multi-level combination HIV prevention interventions that are delivered in youth-friendly mobile settings in an integrated services approach. Details of the mobile health event are outlined in the procedures section (section 7) and the rationale is in section 7.4.

Figure 1: Gender-Age Specific HIV Prevalence (KAIS, 2014)

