11.3 Eligibility Determination (Inclusion/Exclusion) and Enrollment

Participants will be screened for eligibility by Research Assistants or other study staff. Participants must meet all inclusion criteria and may not meet any exclusion criteria in order to be eligible to participate in the study.

Eligibility Requirements:

Inclusion Criteria:

- Female between the ages of 15-24.
- Able to understand spoken English or Kiswahili or Dholuo.
- Resides in Homa Bay County.
- Not previously diagnosed as HIV positive.
- Willing to give informed consent or if younger than 18 years of age and not an emancipated minor, has a parent or guardian willing to provide consent in addition to the minor's assent.

Exclusion Criteria:

- Male.
- Unable to understand spoken English, or Kiswahili or Dholuo.
- Females who are older or younger than the ages of 15-24.
- Resides outside of Homa Bay County.
- HIV positive.
- If under 18 and not an emancipated minor, unable to get parental consent.

Enrollment

After eligibility is assessed/confirmed, participants will be offered enrollment using the approved recruitment script. If she agrees, she will be taken through the following study enrollment procedures: (1) completing registration (to generate a study ID and to ensure single enrollment); and (2) completing the baseline behavioral survey using the tablet computer. Once enrolled, the participant will choose her preferred HIV testing options: (1) oral fluid HIV self-testing at her convenience, (2) HIV testing services (HTS) by study staff at the recruitment location, or (3) a referral to a health care facility for standard HTS. Participants who elect self-testing will be given the self-test kit and will be taken through the self-testing counseling using visual aids (either in the home or in the community). For participants who select staff administered HTS, the test will be conducted by the study staff. For participants who request a referral for HTS at a health facility, they will be given a referral card with the name of a staffer (or other contact to be determined) at the facility. All participants will complete the participant assessment tracking form (this includes locator information for follow-up).

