11.4 Two 'seek' recruitment strategies

Participants for this study will be recruited from either their homes or from a community-based venue. The purpose is to identify which recruitment venue gives the highest yield of HIV infected and at risk female youth. The sample will be stratified by the 3 selected sub-counties; Homa Bay municipality, Mbita and Ndhiwa sub-counties. Approximately four hundred (400) participants will

be recruited from each stratum and for each stratum it is assumed that approximately 200 participants will be recruited through each recruitment approach. Both recruitment strategies (household and mobile community-based event) will run concurrently until the desired target of N=1,200 female youths are enrolled in order to identify N≈108 HIV positive females. See Figure 4, Recruitment Strategy (note: numbers are an approximation).

[figure not shown]
[figure not shown]

Figure 4: Recruitment Strategy

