15.11 Sample Size Considerations

Baseline sample size calculation

Based on our experience with MP3 Youth (data not yet published), which screened N=788 female youth and enrolled N=690 female youth over a period of eight months (November 19, 2014 – June 12, 2015), we expect we can recruit N=1200 female youth over a period of around twice that time. We expect the sample accrual rate to be slower than in MP3 Youth, because we will be recruiting only female youth and mainly those out of school (a large proportion of younger MP3 Youth girls were in school and easier to recruit). In addition, we have two different recruitment strategies, and the home-based strategy may be more labor intensive and time consuming than a community mobile event. We therefore expect a somewhat lower accrual rate. Therefore, in order to stay within the estimate 12 months of recruitment, we will increase our field staff during the implementation phase of the project. Sample size estimates are also based on IRDO's program data and the estimated number of youth in Homa Bay. We expect large numbers of youth will be successfully recruited from the home and mobile events (IRDO reaches tens of thousands of youth/year) for a total sample size of ≥ 1200 female youth.

Power Analysis

Power calculations for Aim 1 are based on the yield of newly diagnosed HIV across recruitment strategies and testing options offered to female youth. Using version 12 of the PASS program (Hintze, 2013) for logistic regression, we did not approach this power analysis from the perspective of calculating a sample size needed to detect a particular effect size with at least 80% power. Rather, because this part of the study (Aim 1) is not a clinical trial but rather an exploration of preferences and yield of recruitment and participant-selected testing strategies, we started with the large, feasible sample size and determined the size of effects that could be detected with at least 80% power when comparing recruitment strategies and HIV testing approaches.

The expected percentage of girls testing positive is based on our MP3 Youth pilot study. In that study, 55 of 636 female youth not previously diagnosed were found to have HIV infection (data not yet published). Thus, we expect about 9% of all tested females in this study to have HIV infection not previously diagnosed.

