With this estimate of the expected percentage of girls with newly diagnosed HIV infection, we asked how small of an increase in the odds of newly diagnosed HIV infection could be detected with 80% power when community-based recruitment is compared to home-based recruitment. With 600 youth recruited by each strategy, power is 80% to detect an odds ratio of 1.67, in other words, a modest increase from 9% to 14% newly diagnosed with HIV infection. When comparing testing approaches, and assuming an equal proportion of girls prefers each approach and testing approach does not interact with recruitment strategy, power is 80% to detect an odds ratio of 1.85. If there is an interaction between recruitment strategy and testing approach, when comparing

testing approaches within a recruitment strategy (i.e., estimating simple main effects), power is 80% to detect an odds ratio of 2.32.

These calculations show the proposed sample size (N=1200) is capable of detecting modest differences in the yield of newly diagnosed HIV infection across both recruitment strategies and testing approaches.

Among the approximately 108 female youth we expect to be newly diagnosed with HIV infection, about 20% are expected to successfully initiate HIV care at a health facility after a single SMS message. The remaining 80% (N=86) who are not linked to care after the initial SMS message will be randomly assigned to either continued SMS messages or to economic incentives. Assuming at least 60% are linked to care at some point during follow-up, survival analysis employing Cox regression will be able to detect a hazard ratio of 2.2 describing the impact of treatment condition (continued SMS vs. economic incentives) on the occurrence and timing of successful linkage to care at a health facility, with 80% power.

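### The Aim 1 yield model does not adjust for sub-county, age, baseline risk or testing history, so the testing-approach odds ratio mixes who chooses a test with any difference due to the test

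*Combined protocol and SAP*

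**What the plan says.** The yield analysis in section 13.2 is a logistic regression of test result on recruitment strategy (home or community) and type of testing (self, staff-aided, facility), with a test of their interaction. Facility testing after community recruitment is the reference, and "we will estimate how home-based recruitment and other testing approaches change the odds of a positive test result".

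Neither exposure is randomised. On testing, section 11.3 says: "Once enrolled, the participant will choose her preferred HIV testing options". The two recruitment strategies run concurrently (sections 10.2 and 11.4), and section 15.12 calls the study observational apart from the linkage pilot in Aim 2a.

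On covariates, section 13.2 does three things:
- It models age, risk behaviours and testing history as predictors of which test a participant prefers.
- In the yield analysis it will consider interactions with those same characteristics. It specifies no model in which they are adjusting main effects.
- It names sub-county in no model, although section 11.4 states: "The sample will be stratified by the 3 selected sub-counties".

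Sections 10.2 and 11.4 target about 400 participants per sub-county, about 200 through each recruitment approach.

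**The concern.** The plan expects age, risk and testing history to drive test choice. Age is also related to HIV status: section 7.2 reports that the "prevalence of HIV among females aged 15-19 is 2.7%, and 20-24 is 6.4" per cent. A variable linked to both the choice of test and the outcome confounds the contrast between tests, and the yield model does not adjust for it.

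Two questions then share one coefficient. The first is which approach finds the most infections among the women who take it up. The second is whether the approach itself alters detection. Crude yield answers the first. The wording about changing the odds suggests the second. If one test is chosen mainly by women aged 20-24, its crude odds ratio rises even when the test makes no difference. Sections 7.1 and 7.3 say the results are to inform scale-up, so advice could credit a test with what is a difference in its users.

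**Working it through.** **Reproducing the plan's detectable odds ratios.** Section 15.11 gives the inputs: "we expect about 9% of all tested females in this study to have HIV infection not previously diagnosed"; "With 600 youth recruited by each strategy, power is 80% to detect an odds ratio of 1.67"; and, for testing approaches in equal thirds (about 400 each), if "testing approach does not interact with recruitment strategy, power is 80% to detect an odds ratio of 1.85". No alpha is stated, so I assume two-sided 0.05. With p1 = 0.09, p2 follows from the odds ratio, and power comes from the pooled two-proportion test.
- OR 1.67: p2 = 14.2%, 600 per group, power 80.0%.
- OR 1.85: p2 = 15.5%, 400 per group, power 79.8%.

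Both stated figures reproduce and can serve as yardsticks.

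**Odds ratio from age mix alone.** Take 2.7% at ages 15-19 and 6.4% at ages 20-24 from section 7.2, and assume no difference between approaches within an age band. With share f aged 20-24, p(f) = (1 - f) × 0.027 + f × 0.064. The crude OR is the ratio of the odds in the older group to the odds in the younger group. The ceiling is the age OR itself: (0.064/0.936) / (0.027/0.973) = 2.46.

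The age splits below are assumptions. The last column scales both prevalences by 0.09/0.0455 = 1.978 (to 5.34% and 12.66%), so that an even age mix gives the planned 9% yield.

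| Share aged 20-24 | Yields, prevalences as given | OR | OR, scaled to 9% |
|---|---|---|---|
| 45% vs 55% | 4.37% vs 4.74% | 1.09 | 1.09 |
| 40% vs 60% | 4.18% vs 4.92% | 1.19 | 1.20 |
| 30% vs 70% | 3.81% vs 5.29% | 1.41 | 1.43 |
| 20% vs 80% | 3.44% vs 5.66% | 1.68 | 1.73 |

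On the prevalences as given, a symmetric split must be about 20.5% vs 79.5% to reach 1.67 (a gap of 59 points) and about 15% vs 85% to reach 1.85. If the younger group already has 40% aged 20-24, the largest possible OR is 1.57 as given (4.18% vs 6.40%), or 1.61 scaled.

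**Effect on false positives.** With the same test and 400 per approach, the chance of a significant result when there is no within-age effect is 8% to 11% for a 40/60 split and 17% to 30% for 30/70, against a nominal 5%. The lower figure uses the prevalences as given and the higher one the scaled values.

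**Sub-county.** With about 200 per recruitment approach in each of three sub-counties, the distribution is the same in both venues, so sub-county cannot confound the venue contrast while those targets hold. Nothing balances it across testing approaches.

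**The case against.** The strongest reply is that crude yield is what the study wants. The objective in section 8 is to find the venue and testing modality that identify the most infected and at-risk youth, and section 11.4 says the same of venue. Reaching older or higher-risk women is part of what a venue does, and adjustment would remove some of the answer. This stands. It is why crude yield should remain the main result and why adjustment matters chiefly for testing approach.

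Sections 10.2, 15.11 and 15.12 also say openly that Aim 1 is exploratory, with participant-selected testing, and that the study is observational outside the linkage pilot. The phrase about changing the odds can be read as ordinary language for a coefficient, since the preference model uses similar words. This reduces the weight of the wording but supplies no adjusted estimate.

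It would also be wrong to say that age, risk and testing history are ignored. Interactions with them are to be considered, and a conventionally specified interaction model carries their main effects. Table 1 lists differences by age and recruitment strategy. What is missing is a defined adjusted estimate for testing approach.

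A reader might infer that age mix alone could produce the odds ratio the study is powered to detect. The documents do not support that. It needs a split near 20/80 for 1.67 and near 15/85 for 1.85, and nothing in the protocol suggests imbalance of that order between groups recruited at ages 15-24 in the same sub-counties over the same period.

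Finally, the prevalences are national and cover all HIV, while the endpoint is new diagnosis with known positives excluded. Section 7.2 reports ever-testing of 55.6% at ages 15-19 and 91.6% at 20-24, so the gradient in new diagnoses could be flatter than 2.46. A steeper local gradient is also possible. The figures in the table are illustrations, not estimates.

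**Conclusion.** The point holds as a gap in pre-specification, mainly for testing approach. The yield model does not adjust for variables that the plan itself treats as drivers of test choice, and it leaves out the sampling stratum, yet its coefficients are worded as effects. Under the stated assumptions (age the only confounder, the section 7.2 gradient as a proxy, hypothetical splits), moderate age imbalance moves the odds ratio to about 1.2 to 1.4. That is enough to raise the false-positive rate above its nominal level, but short of the detectable 1.67 and 1.85. Risk behaviour and testing history could add to this or offset it, and the documents give no figures to size them. For venue, the crude comparison answers the stated objective, and sub-county is balanced by design if the recruitment targets are met.

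**What to change.** In section 13.2:
1. Keep crude yield by venue and by testing approach as the answer to which finds the most infections, and describe the crude odds ratios as associations.
2. Add sub-county as a fixed effect in the Aim 1 models. This matters mainly for testing approach, and for venue if the 200/200 targets are missed.
3. Pre-specify a second yield model with age, baseline risk and prior testing as main effects, used chiefly for the testing-approach contrast. Rest any statement beyond association on that model, with the caveat that self-selection on unmeasured factors remains.

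The cost is mostly SAP wording. Demographics and risk behaviours are in the baseline interview, and section 13.2 already plans to use testing history as a predictor of test choice. The downside is two odds ratios per comparison, so the text must say which question each one answers.
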